Aim 3) To characterize neural functional deficits and/or abnormalities in youth with ASD by comparing ASD subjects to healthy control subjects undergoing the same spectroscopic & RsFc imaging with two scans 12 weeks apart.

III. LENGTH OF STUDY

This study may take up to 20 weeks from enrollment (allowing up to eight weeks to schedule and complete the initial screening process and baseline scan). Once subjects have completed the screening process and baseline characterization, subjects eligible for scanning will complete a baseline scan (for ASD subjects, this scan will be pre-treatment). ASD subjects will then begin the 12-week randomized-controlled trial. All subjects eligible for scanning, including healthy controls, will receive a follow-up scan approximately 12 weeks after the baseline scan. For ASD subjects, this scan will take place between the 10th and 12th week of treatment. All subjects will be taking the study medication at the time of the second brain scan. ASD subjects ineligible for scanning may participate in the 12-week randomized-control phase of the trial only.

IV. SUBJECT SELECTION CRITERIA

A. Inclusion Criteria (all participants)

1. Male & female subjects ages 8-18 years (inclusive).

Participants with ASD

- 3. DSM-5 ASD diagnostic criteria as established by clinical diagnostic interview
- 4. At least moderate severity of social impairment as measured by a total raw score of ≥85 on the parent/guardian-completed Social Responsiveness Scale-Second Edition (SRS-2)⁷¹ and a score of ≥4 on the clinician-administered Clinical Global Impression-Severity scale (CGI-S).

Healthy Control Participants

- 3. Age-, sex-, & IQ-matched with ASD participants.
- No Axis I diagnoses as established by the Kiddie Schedule for Affective Disorders and Schizophrenia—Epidemiological Version (K-SADS-E)⁷⁰ & confirmed by clinical diagnostic interview.
- 5. No significant traits of ASD as screened by SRS-2 (raw score <60).

Exclusion Criteria (all participants)

- 1. IQ ≤70 based on the Wechsler Abbreviated Scale of Intelligence-II (WASI-II) Vocabulary and Matrix Reasoning subtests
- 2. Impaired communicative speech
- 3. Subjects currently treated with the following medications (known to impact glutamate levels):
 - a. Lamotrigine
 - b. Amantadine

- c. N-acetylcysteine
- d. D-cycloserine
- 4. Subjects treated with a psychotropic medication not listed above on a dose that has not been stable for at least 4 weeks prior to study baseline.

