Participating children and adolescents with ASD who meet the eligibility criteria will be randomly assigned to either memantine or placebo for the course of the 12-week RCT. Subjects will be assessed weekly during the titration phase (Weeks 1-4) & during the maintenance phase at midpoint (Week 6), Week 9, & at completion (Week 12/early termination). The same caretaker (a parent/guardian most familiar with the subject's day-to-day behavior) will participate in the assessment of behavioral symptoms at all visits of the treatment phases.

Randomization: The MGH Clinical Trials Pharmacy will prepare the blinded

memantine and placebo capsules for the study. ASD subjects will be randomized to either active memantine or placebo in a 1:1 ratio after they have been determined to meet all eligibility criteria. Randomization lists stratified by gender and racial/ethnic minority status (minority vs. Caucasian) will be generated by the statistician & passed to the investigational pharmacy for assignment.

Washout Period: ASD subjects who are currently being treated with prohibited psychotropic medications as listed in the exclusion criteria must discontinue the use of their medication to be eligible for participation in this study. Medication washout is recommended by our clinicians to participants, their parent/guardian, and current providers – this is done based on a case-by-case assessment, considering the duration on drug, the dose, and the adverse effects associated with the treatment and effects of stopping that medication/treatment. Our office does not take over care for the patient, but remains available during this time period. The washout schedule –which will span two weeks or more -- will be discussed with the participant, their parent/guardian, and current providers. Individuals taking a medication that is effectively and safely treating their symptoms will not be taken off of such medication for the purpose of enrolling in this study.

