If study participation is discontinued due to safety reasons, participants will receive three follow-up visits, giving adequate time for appropriate psychiatric referrals to treaters in their community. If emergent suicidality were to occur during the course of the study, the supervising clinician will then directly assess the level of risk and take the appropriate action (including contacting treatment providers, working on a safety plan, arranging for emergency evaluation via an ER, calling 911, etc.) The clinician will document the actions taken, and it will be noted in the participant's file. Subjects who discontinue due to non-compliance with the protocol will receive a referral to ASD treaters in the area.

¹HMRS Scanning (ASD and Healthy Control Subjects):

All subjects eligible for scanning will complete two scanning sessions at the McLean Imaging Center over the course of the study. For subjects with ASD, the initial scan will take place after evaluation and screening and prior to randomization. ASD participants will have a second scanning session at McLean between the 10th and 12th week of treatment.

Upon signing consent/assent at MGH, healthy control subjects will participate in screening procedures to assess eligibility. Those who meet eligibility criteria and complete screening procedures will participate in two scanning sessions at McLean Imaging Center. The first scanning session will take place after screening procedures are completed at MGH, and the second scanning session will take place approximately 10-12 weeks after the first.

During the first scanning visit, subjects will undergo a urine drug screen to determine recent drug use, and all women of childbearing potential will be asked to undergo a urine pregnancy screen. A breath sample will be obtained to screen for alcohol. These procedures will be repeated when subjects return to complete for their second scanning visit. Additionally, parents/guardians of all eligible subjects will complete the Child Behavior Checklist (CBCL) during the first scanning visit at McLean Imaging Center in order to assess the child's maladaptive emotional and behavioral problems at the time of the scan.

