After the 2D-JPRESS dataset is resolved into a series of one-dimensional spectra where each spectrum is modeled and fitted with GAMMA simulated J-resolved basis sets, Glu levels will be derived from the total integral across the J-series. Glu transverse relaxation time (T2) will be obtained from the raw peak vs. TE decay curve fitted with

Levenberg-Marquardt algorithm using an exponential decay function (for Glu T2) convoluted with a polynomial function (for Glu J-coupling) that will be obtained from the GAMMA simulation run with previously measured spectral parameters. Data quality will be assessed by LCModel calculated Full Width Half Maximum (FWHM), Signal to Noise Ratio (SNR) and Cramer-Rao Lower Bounds (CRLB).

The following brain measures will be examined between groups and withinsubject across time (e.g., pre- versus post-treatment and correlations between the measures of brain activity and clinical features):

1) ¹HMRS measures of brain Glu in:

a) ACC

b) MTL

2) measures of resting state functional connectivity of:

- a) dorsal & ventral ACC with prefrontal cortex including VMPFC;
- b) bilateral amygdala with insula & VMPFC;

c) bilateral hippocampus with posterior cingulate cortex.

Pretest-posttest brain activity differences will be analyzed using linear regression models, where treatment group is the primary predictor and pretest measures of brain activity are covariates. A general linear regression model will evaluate the difference between the treatment groups in posttest brain measures while controlling for each subject's pretest measures of brain activity. This approach is equivalent to analyses of covariance (ANCOVA). We will also test if changes in Glu in memantine and placebo (PBO) responders differ from changes in Glu over time in healthy controls (HCs). This requires a three-group comparison: memantine responders vs. PBO responders vs. HCs. We will use a GLM to compare Glu changes from baseline to endpoint. If the direction and magnitude of change among the three groups are the same, there will be no group by time interaction. If the interaction is significant and responders show greater changes compared to HCs, it will indicate that the changes observed in responders are greater than expected from normal changes in Glu activity. We will do follow-up tests to separately test the interactions for each pair of the three groups analyzed.

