We also predict normalization of brain activity measures with memantine treatment. "Normalization" will be defined as having achieved a resting state functional connectivity level that is no more extreme than the 95th percentile of the control distribution. Normalization ratings between the memantine and PBO groups will be compared using a logistic RMs. A significant effect would mean an increased likelihood of normalization in memantine-treated subjects.

To test our hypothesis of a significant association between neural and clinical response and between glutamate and functional connectivity response, we will use endpoint clinical efficacy scores as the dependent variable and change in brain activity measures from baseline to endpoint as the independent variables. For our exploratory hypothesis examining neural biomarkers of response to memantine therapy, we will use a GLM with endpoint clinical efficacy scores as the dependent variable, baseline brain activity measures as the independent variables, and baseline clinical scores as a covariate.

Resting state data will be analyzed using a seed driven approach with custom software (Conn)⁸⁸. Data will be slice time corrected, realigned, coregistered, normalized, and spatially smoothed as necessary. Physiological & other spurious sources of noise

will be estimated using the CompCor method, and removed together with movementrelated covariates. The residual BOLD time-series will be band-pass filtered over a lowfrequency window of interest (0.009Hz<f<0.08Hz). Correlation maps will be produced by extracting the residual BOLD time course from bilateral anatomically defined amygdala (WFU_Pickatlas) seed regions, and computing Pearson's correlation coefficients between that time course and the time course of all other voxels. Correlation coefficients will be converted to normally distributed scores using Fisher's transform to allow for second-level General Linear Model analyses. Between group differences will be calculated for each ROI.

Power Considerations

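### The normalization endpoint ignores the baseline scan, so an arm's rate mixes conversion with having been in range all along, and the unadjusted logistic test is weak

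*Combined protocol and SAP*

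**What the plan says.** Under Neuroimaging Data Analysis the plan predicts that memantine will normalize brain activity measures. It defines normalization as "having achieved a resting state functional connectivity level that is no more extreme than the 95th percentile of the control distribution". The analysis is one sentence: "Normalization ratings between the memantine and PBO groups will be compared using a logistic RMs". The reading of a positive result follows: "A significant effect would mean an increased likelihood of normalization in memantine-treated subjects".

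The verb in the definition hints at change, but nothing puts that into effect. No out-of-range value at baseline is required, and no baseline covariate or subset is named for the logistic model.

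Four other places bear on this:

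- Subject Selection Criteria select ASD subjects on clinical severity ("At least moderate severity of social impairment as measured by a total raw score of ≥85" on the SRS-2, plus a CGI-S threshold) and set no connectivity threshold.
- Under ¹HMRS Scanning, "the initial scan will take place after evaluation and screening and prior to randomization", so each scanned subject's baseline status is known before allocation.
- Under Randomization, "ASD subjects will be randomized to either active memantine or placebo in a 1:1 ratio".
- Earlier in Neuroimaging Data Analysis, the resting-state connectivity measures are to be analysed by linear regression "where treatment group is the primary predictor and pretest measures of brain activity are covariates", that is, by ANCOVA.

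**The concern.** The word normalization says that something abnormal became normal. The rule scores only where the subject ends up. If most ASD subjects lie inside the control range before treatment, most of the events in either arm will be subjects who had nothing to normalize. A report that, say, 70% of an arm normalized would then mislead, even if the comparison between arms is sound.

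There is also a loss of power. When most placebo subjects are in range anyway, the memantine rate has little room to rise, and cutting a continuous measure in two discards information. The baseline scan, which would recover part of this, is collected but not used in this model. A null result on a stated prediction could then say very little.

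**Working it through.** **Inputs from the documents.** 40 randomized ASD subjects, 1:1, so at most 20 per arm (fewer if some cannot be scanned); 20 healthy controls; 95% power stated for the ASD (40) versus control (20) connectivity difference under Power Considerations. No connectivity effect size, alpha or sidedness is given.

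**Assumptions.** Normal data, equal SDs, ASD mean shifted d SD above controls (the plan reports hyperconnectivity), two-sided alpha 0.05, correlation of 0.5 to 0.7 between the two scans.

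**1. The plan's own figures.** Two-sample noncentral t power at 7 versus 7 gives 0.541, 0.426 and 0.507 for d = 1.20, 1.03 and 1.15. The plan states 0.55, 0.43 and 0.51 for spectroscopy, so the method agrees. The 95% for connectivity cannot be reproduced without an effect size, but it can be inverted. The normal approximation gives d = (1.960 + 1.645) × √(1/40 + 1/20) = 3.605 × 0.274 = 0.99; the noncentral t gives 1.00.

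**2. Share of ASD subjects in range before treatment.** One-sided limit: Φ(1.645 − d). Two-sided limit: Φ(1.96 − d) − Φ(−1.96 − d).

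| d | One-sided | Two-sided |
|---|---|---|
| 0.5 | 87% | 92% |
| 0.8 | 80% | 87% |
| 1.0 | 74% | 83% |
| 1.5 | 56% | 68% |
| 2.0 | 36% | 48% |

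At d = 1.0 and a one-sided limit, about 40 × (1 − 0.74) = 10.4 subjects, or about 5 per arm, are out of range at baseline.

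**3. Estimating the limit from 20 controls.** The sample 95th percentile of 20 values has a simulated median of 1.41 SD and a 95% range of 0.71 to 2.28 SD, that is, roughly the 76th to the 99th true percentile. At d = 1.0 the share in range at baseline then runs from 38% to 90%. In simulation at d = 1.0 to 1.2, 58-67% of placebo subjects are scored as normalized, and 67-82% of all subjects so scored were in range at baseline.

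**4. Validity of the comparison between arms.** With no drug effect, the comparison of all subjects rejects in 4-6% of runs (chi-square). Subjects in range at baseline do not create a false effect.

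**5. Power at 20 per arm, 0.8 SD drug effect, d = 1.0 to 1.2.**

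| Analysis | Power |
|---|---|
| Logistic, unadjusted (as planned) | about 39-45% |
| Logistic with baseline connectivity | 48-57% |
| ANCOVA on the continuous measure (also planned) | 79-92% |

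The adjusted logistic model has a type I error of about 6-7% at this sample size, so a small part of its gain is not real.

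**6. Restricting to subjects out of range at baseline.** At d = 1.0 with complete normalization, chi-square power falls from 45-47% (all subjects) to 21-31%. Regression to the mean also puts 39-52% of the out-of-range placebo subjects back in range at endpoint.

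**The case against.** A reader might go further and infer that the endpoint cannot show any effect of memantine on connectivity, or that the plan's reading of a significant result does not follow at all. The documents do not support that. Allocation is randomized 1:1 after the baseline scan, so subjects in range at baseline are balanced in expectation. A true difference between arms has to come from more conversions on memantine or fewer exits from the range, and both are drug effects. In simulation at d = 1.2 with a 0.8 SD effect, 55-61% of the difference came from conversions and the rest from prevented exits. The make-up of all events is a different matter from the source of the difference.

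The main inference is also protected: the plan already analyses the same measures by baseline-adjusted ANCOVA, which is far stronger, and the dichotomy adds description. Restricting the analysis to subjects abnormal at baseline is a tempting remedy, but it loses power and its rate is inflated by regression to the mean. Error in the control limit applies equally to both arms and does not bias their comparison.

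All of this stands. It leaves two things untouched: an arm's rate does not mean what its name says, and the logistic model leaves out a covariate that is already in hand.

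**Conclusion.** The point holds as a matter of interpretation and efficiency, not of validity. The definition does not separate conversion from having been in range before treatment. At d of about 1.0, roughly three quarters of ASD subjects or more (74% one-sided, 83% two-sided, with an exactly known limit) would meet it before the first dose, so an arm's rate cannot be reported as a normalization rate. The memantine-placebo difference remains a valid randomized contrast, in being within range at endpoint. The planned test has less than an even chance of detecting a 0.8 SD effect.

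These sizes rest on assumptions that the documents do not supply: d, alpha, normality, equal SDs and the correlation between scans. At d = 2.0 only 36-48% would be in range at baseline, so the statement that most are already in range would no longer hold. An imaging sample below 40 would lower every power figure. The primary clinical outcomes are not affected.

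**What to change.** In Neuroimaging Data Analysis:

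1. Keep all scanned randomized subjects and rename the endpoint *within control range at endpoint*.
2. Add the baseline connectivity value as a covariate in the logistic model.
3. State that the claim of a drug effect on connectivity rests on the ANCOVA already planned.
4. Report conversion among subjects out of range at baseline by arm, with the number at risk, as description only, and note that regression to the mean will produce conversions on placebo too.
5. State whether the limit is one- or two-sided, which of the two control scans sets it, and how the several connectivity measures are handled.

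The cost is a few sentences, with no new data. The downside is that logistic regression with a covariate in about 40 subjects is slightly anti-conservative (type I error about 6-7%); a penalized-likelihood or exact method can be specified to deal with this.

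Replacing the raw percentile by the control mean plus 1.645 SD is optional. With 20 controls it narrows the limit's 95% range only from the 76th-99th to the 83rd-99th true percentile, and it relies on normality of the control values.

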Brain regions implicated in Autism: Several studies aiming to identify the etiology of autism have indicated involvement of limbic system structures including the amygdala, hippocampus, & the ACC⁴¹⁻⁴³. These limbic structures also show a high affinity for NMDA receptor binding. ACC: is functionally associated with information processing and response to emotional cues and is, therefore, a region of interest in autism. The ACC also has close anatomic connections to the amygdala & participates in emotional regulation. Lesions of ACC are known to cause blunted affect, disinhibition, disabling repetitive behaviors, & impaired social judgment including the inability to interpret social cues⁴⁴. Converging evidence from various investigative modalities suggests abnormalities in the ACC region in individuals with ASD including histopathological changes of increased cell packing density & decreased cell size, smaller in volume, decrease in regional cerebral blood flow, & metabolically less active^{34-35, 38, 39-40} with abnormal functional activity (theory of mind task related & resting state)⁴⁵⁻⁵². MTL: structures, the hippocampus & amvadala, play crucial roles in associative memory & social cognition, respectively, & lesions in the MTL are implicated in social impairments intrinsic to ASD⁵³⁻⁵⁵. Converging evidence of abnormalities in the MTL in ASD comes from various histopathological & imaging studies revealing decreased neuronal size and increased cell density and cytoarchitectural minicolumnar pathology, bilateral decreased volume & hypo-perfusion, and abnormal activation especially of amygdala on face recognition41,45-46,48, 55-65.

II. SPECIFIC AIMS

Primary Aims

Aim 1) To examine the clinical efficacy & tolerability of memantine for the treatment of social impairment in youth with ASD. We will study the short- & long-term clinical effects of memantine in 40 children and adolescents with ASD by conducting a 12-week randomized-controlled trial (RCT).

Aim 2) To examine the effect of memantine therapy on neural function in youth with ASD. We will assess neural response to memantine therapy by measuring spectroscopic

& resting state functional connectivity (RsFc) changes with memantine treatment. We will also assess association of neural & clinical response to memantine therapy.

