Dose Titration Phase (Weeks 1-4): Study medication will be initiated at 2.5 mg/day, will be raised to 5 mg/day on day 4, and will be gradually up-titrated by 5 mg/week to a maximum dose of 20 mg/day. Titration of the study medication will be guided by the (following) forced titration schedule with an option for slower titration or holding at lower dose per clinician judgment. Memantine will be administered in twice daily divided dosages with a total daily dose of \geq 2.5 mg/day.

Study Medication Dosing: Study medication (memantine/placebo) will be titrated to the maximum daily dose during the first 4 weeks of the trial (dose titration phase). Subjects will follow the following forced titration schedule until Week 4 when subjects will be maintained on maximum achieved dose until the end of the trial (dose maintenance phase; Weeks 5-12). During the dose maintenance phase, there will be a one-time option to decrease the dose of the study medication.

Mema	antine Forced	Titration Schedule
Visit	Day	Maximum Total Dose Prescribed (mg/day)
0	1	2.5
	5	5
1	8	10
2	15	15
3	22	20
4	28	Maintained on maximum achieved dose

Primary Outcome Measure of Efficacy: Clinician-rated CGI-Improvement (CGI-I) subscale and the parent-rated SRS-2. Treatment responders will be defined as those who demonstrated improvement of ≥25% on the SRS-2 total raw score *and* a score of 2 or 1 on the CGI-I subscale ("much" or "very much improved").

Secondary Outcome Measures of Efficacy: As with other psychotropic treatment outcomes in this population⁷², response to memantine may not be uniform for all domains of ASD. The response differential will be examined by assessing change in the severity of the subscales of the SRS-2 representing core domains of ASD, change on the ABC-SW subscale, and change on the MGH-ASD-RS (clinician- and informant-rated). The CY-BOCS-PDD⁷³⁻⁷⁴ will be administered to assess change with treatment in the ritualistic behaviors associated with ASD. Change with treatment in the level of adaptive functioning will be assessed by the CBCL. Change in the level of global functioning will be assessed by the parent/guardian-rated SAICA. Considering that features of ADHD, anxiety, & depression are frequently associated with ASD⁴ & there is evidence of memantine's effectiveness in treating ADHD in adults, these symptoms will be assessed by administering the clinician-rated ADHD-SCL, CDRS-R⁷⁹, & CASI-Anx⁸⁰.

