- Child Behavior Checklist (CBCL)⁸⁸ is a parent-report questionnaire that evaluates maladaptive behavioral and emotional problems, both internalizing and externalizing, in children ages 6-18.
- Social Adjustment Inventory for Children and Adolescents (SAICA)⁸⁹ is a semistructured interview administered to the child or parent/guardian that assesses social functioning in children 6-17 years old. Content areas include activities, peer relations, family relations, and academic performance (John et al., 1987).
- MGH- Social Emotional Competence Scale-Informant Rated (MGH-SECS-I): This is a 37-item scale that asks informants to rate subjects on their social competence and abilities on a Likert scale from 0 to 6.

• Pre-MR Checklist: This checklist reviews basic medical history that may be pertinent to MR scanning and potential MR contraindications including metallic implants or claustrophobia.

Clinician Rated:

Clinical Global Impression Scale (CGI)87

 The CGI is a measure of illness severity, improvement, and efficacy of treatment (National Institute of Mental Health, 1985). The score for severity ranges from 1 (normal, not at all ill) to 7 (among the most extremely ill subjects). Improvement ranges from 1 (very much improved) to 7 (very much worse). And lastly, the effectiveness index measures to what extent the subject is experiencing therapeutic effects as well as the level of adverse events they are experiencing. The CGI scale will be used for the assessment of global functioning. Additionally, the following disorder-specific CGIs will also be administered: ASD, ADHD, OCD, psychosis, mania, depression, and anxiety.

Depression

- The Children's Depression Rating Scale (CDRS)⁷⁹ is a widely used observational rating measure of depression severity in children and adolescents.
- CGI-Depression.

Anxiety

- Children and Adolescent Symptom Inventory-5 Anxiety Scale (CASI-Anx)⁸⁰
- CGI-Anxiety.

ADHD

- ADHD Symptom Checklist assesses each of the individual symptoms of ADHD based on the DSM (0-3 on a scale of severity)
- CGI-ADHD.

Psychosis

• CGI-Psychosis.

Obsessive-Compulsive Disorder (OCD)

- The Children's Yale Brown Obsessive Compulsive Scale for PDD (CY-BOCS-PDD)⁷⁴ will be used to assess obsessive and compulsive symptoms. This is a clinician-rated 10-item scale (total range from 0 to 40), with subtotals for obsessions (items 1-5) and compulsions (items 6-10).
- CGI-OCD.

Autism Spectrum Disorder (ASD)

CGI- ASD

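### The glutamate–connectivity hypothesis is given a model with a clinical score as outcome, which cannot test it; for severity scales the same model also leaves out the pre-treatment score

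*Combined protocol and SAP*

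**What the plan says.** Neuroimaging Data Analysis states one hypothesis with two parts and one model for both. The text reads "association between neural and clinical response and between glutamate and functional connectivity response, we will use endpoint clinical efficacy scores as the dependent variable", with "change in brain activity measures from baseline to endpoint as the independent variables". No covariate is named.

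The next sentence, on exploratory biomarkers, does name one: "baseline brain activity measures as the independent variables, and baseline clinical scores as a covariate".

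Earlier in the same section, group differences in each brain measure are analysed by ANCOVA, "where treatment group is the primary predictor and pretest measures of brain activity are covariates". Glu change is compared across memantine responders, placebo responders and healthy controls. The only correlations mentioned are "correlations between the measures of brain activity and clinical features". Aim 2 likewise promises only the neural–clinical link: "We will also assess association of neural & clinical response to memantine therapy".

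The model does not say which clinical score it uses. Under Primary Outcome Measure of Efficacy the measures are "Clinician-rated CGI-Improvement (CGI-I) subscale and the parent-rated SRS-2". It also does not say whether the two ASD arms are pooled.

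**The concern.** The second hypothesis is about two brain measures changing together. A regression with a clinical score on the left-hand side treats them as fellow predictors, so it answers a different question. If the plan is followed literally, a stated hypothesis goes untested, or a coefficient from the clinical model is read as evidence on it. If the analyst improvises instead, the Glu region, connection pair, handling of baseline and arm adjustment are all chosen after the data are seen. The plan lists two Glu regions and several connection pairs.

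The smaller concern is the first hypothesis. With a severity scale such as SRS-2 as outcome and no pre-treatment score, the model relates brain change to final severity rather than to response. That costs precision in a small scanned sample. It can also produce false positives if brain change is related to how severe the child was at the start.

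**Working it through.** **1. What each planned analysis estimates**

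| Analysis (Neuroimaging Data Analysis) | Outcome | Predictors | Glu–connectivity association? |
|---|---|---|---|
| ANCOVA | Post-treatment brain measure | Arm, its own pretest | No, an arm effect |
| Three-group comparison | Glu change | Responder/control group | No |
| Correlations | Brain measure with clinical feature | – | No |
| Association model | Final clinical score | Brain changes | No |
| Exploratory model | Final clinical score | Baseline brain, baseline clinical | No |

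Write the association model as C1 = b0 + b1·ΔGlu + b2·ΔFC + e, where FC is functional connectivity. Both b1 and b2 are links to C1. The correlation of ΔGlu with ΔFC affects their standard errors but is not a parameter of the model. The lead point follows from this form alone and needs no assumed values.

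**2. Size of the mismatch**

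The plan gives no sample size or power for these associations, so there is no figure to reproduce. I simulated ordinary least squares with 20,000 runs per case, two-sided 5% tests and standardised variables. Inputs from the documents are 40 randomised ASD subjects (Source of Subjects), and fewer scanned, because subjects with MR contraindications may join the drug trial only. n=30 is my assumed lower case. Every correlation, slope and shift below is also assumed.

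Model: FC1 = 0.5·FC0 + s·ΔGlu + e, with unit variance.

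| Case | s=0 | s=0.3 | s=0.5 |
|---|---|---|---|
| Planned model, either coefficient, score unrelated to brain change, n=40 | 5% | 5% | 5% |
| FC1 on ΔGlu, FC0 and arm, n=40 | 5% | 58% | 98% |
| Same, n=30 | 5% | 45% | 92% |

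Conversely, take s=0 with connectivity change correlated 0.4 with the clinical score. The planned connectivity coefficient then rejects about 74%.

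**3. Why the replacement needs baseline Glu**

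In step 2, Glu change was simulated as independent of baseline. Suppose instead that half the connectivity variance is a stable trait, Glu retest correlation is 0.5, and the two changes are unrelated. If baseline Glu correlates 0.3, 0.5 or 0.7 with the trait, FC1 on ΔGlu and FC0 rejects about 6%, 10% and 14% at n=40. With baseline Glu added it rejects 5%.

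**4. Pre-treatment score, severity scales only**

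Model: Y = r·B + 0.3·D + e with unit variance, where B is the pre-treatment score and D the brain change, n=40. The large-sample test ratio is 0.3·√40 / residual SD = 1.90 / residual SD.

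- Without B: residual SD = √(1 − 0.09) = 0.954, ratio 1.99.
- With B, r=0.4: √(1 − 0.16 − 0.09) = 0.866, ratio 2.19.
- With B, r=0.6: √(1 − 0.36 − 0.09) = 0.742, ratio 2.56.
- With B, r=0.8: √(1 − 0.64 − 0.09) = 0.520, ratio 3.65.

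Simulated power is about 48% without B, and 54%, 67% and 92% with it. At n=30 it is 37% against 42%, 53% and 82%.

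Type I error without B (r=0.6, n=40) is 5%, about 9% and about 20% when D correlates 0, 0.15 and 0.3 with B. With B it is 5% throughout.

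**5. Treatment arm**

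If the drug shifts both D and Y by 0.5 or 0.8 SD with no link within arms (r=0.6, n=40), the planned pooled model rejects 6% or 14%. With the pre-treatment score and arm it rejects 5%. Adding arm costs about 1 point of power if the drug does not move the brain predictor. It costs about 4–8 points at a 0.8 SD shift and 6–13 at 1.1 SD. The last value borrows the d=1.10 that Power Considerations gives for Glu change in the ASD group; using it as a between-arm shift is my assumption.

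**The case against.** The Glu–connectivity hypothesis occupies one clause. Aim 2 does not mention it, the list containing the correlations is introduced only by way of example, and any analyst would simply correlate the two changes. That limits the weight of the point but does not remove it: the plan does name a model for this hypothesis, and it is one that cannot answer it.

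The missing pre-treatment score is read from silence. The clinical score is not named, and the plan's responder definition uses CGI-I and percentage change in SRS-2, both already change-based. This stands in part. CGI-I rates improvement directly and needs no baseline. For severity scales the contrast with the adjacent sentence makes the silence meaningful.

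Arm adjustment is not a free correction. It removes co-change caused by the drug, which is arguably part of response to memantine. This stands: whether to adjust depends on the association wanted, so both results belong in the report.

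A reader might go further and infer that the neural–clinical test is invalid. The documents do not support that. If brain change is unrelated to baseline severity, the test is valid and only power is lost, and nothing in the documents says they are related.

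**Conclusion.** The point holds. As written, the stated Glu–connectivity hypothesis has no test anywhere in the plan, and the model assigned to it can be null when the two measures change together and significant when they do not.

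The second part holds for SRS-2 and other severity scales only. The expected gain is power, roughly 6 to 44 points at n=40 (54 − 48 to 92 − 48) over the assumed correlations. Protection against false positives is added only if brain change is related to baseline severity.

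If the analysis is meant for memantine-treated subjects alone, 1:1 allocation of 40 leaves at most about 20. At n=20, power for a Glu–connectivity slope of 0.3 is about 32% without arm. The severity-scale model has about 25% without the pre-treatment score and 28–61% with it.

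It would be wrong to infer that the efficacy conclusion is at risk. This is a mechanistic analysis, separate from the primary efficacy test and from the imaging ANCOVA. It should be corrected before the data are analysed.

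**What to change.** 1. Write a separate model for the second hypothesis: follow-up connectivity as outcome, Glu change as predictor, baseline connectivity and baseline Glu as covariates. Name one Glu region and one connection pair as the main test.
2. State whether the ASD arms are pooled. If they are, report the model with and without treatment arm. Say that the adjusted one gives the within-arm association and the unadjusted one also includes drug-induced co-change.
3. Name the clinical score in the neural–clinical model. For SRS-2 and other severity scales, add the pre-treatment score. CGI-I needs none. For SRS-2 this is the screening form, since Table I schedules none at baseline. Take it from the caretaker who rates at Week 12 where available, because Study Procedures lets both parents complete a form and uses the higher for eligibility. Flag any case where another form is used.

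Cost: SAP wording, one added regression and one or two degrees of freedom, with no new data. Two precision costs should be acknowledged. Arm adjustment costs what step 5 shows. Baseline Glu overlaps with Glu change: with equal variances and the assumed retest correlation of 0.5, it shares 25% of the variance of Glu change. The standard error then rises by up to 1/√0.75 = 1.15, roughly as if n fell from 40 to 0.75 × 40 = 30, less whatever baseline Glu explains of the outcome.
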